## MEDICAL PROTOCOL (HRP-590)

PROTOCOL TITLE: Combining cerebellar tDCS and constraint-induced language therapy in non-fluent aphasia: a novel approach to target discourse  
 VERSION DATE: 08/09/2023

### ANCILLARY REVIEWS

**DO NOT DELETE.** Submit the completed checklist below with your protocol.

Which ancillary reviews do I need and when do I need them? Refer to HRP-309 for more information about these ancillary reviews.			
Select yes or no	Does your study...	If yes...	Impact on IRB
 Yes  No	Include Gillette resources, staff or locations	Gillette Scientific review and Gillette Research Administration approval is required. Contact: [contact]	Required prior to IRB submission
 Yes  No	Involve Epic, or Fairview patients, staff, locations, or resources?	The Fairview ancillary review will be assigned to your study by IRB staff Contact:	Approval must be received prior to IRB committee/ designated review.
 Yes  No	Include evaluation of drugs, devices, biologics, tobacco, or dietary supplements or data subject to FDA inspection?	The regulatory ancillary review will be assigned to your study by IRB staff Contact: [contact] See: https://policy.umn.edu/	Approval must be received prior to IRB committee/ designated review.
 Yes  No	Require Scientific Review? Not sure? See guidance in the Investigator Manual (HRP-103).	Documentation of scientific merit must be provided. Contact: [contact]	Consider seeking approval prior to IRB submission.
 Yes  No	Relate to cancer patients, cancer treatments, cancer screening/prevention, or tobacco?	Complete the CPRC application process. Contact: [contact]	Consider seeking approval prior to IRB submission.
 Yes  No	Include the use of radiation? (x-ray imaging, radiopharmaceuticals, external beam or	Complete the AURPC Human Use Application and follow instructions on the form for submission to the AURPC committee.	Approval from these committees must be received prior to IRB approval.
 Yes  No	Use the Center for Magnetic Resonance Research (CMRR) as a study location?	Complete the CMRR pre-IRB ancillary review Contact: [contact]	Approval from these committees must be received prior to IRB approval.

## MEDICAL PROTOCOL (HRP-590)

PROTOCOL TITLE: Combining cerebellar tDCS and constraint-induced language therapy in non-fluent aphasia: a novel approach to target discourse

VERSION DATE: 08/09/2023

 Yes  No	Include the use of recombinant or synthetic nucleic acids, toxins, or infectious agents?	Complete the IBC application via eprotocol.umn.edu	These groups each have their own application process.
 Yes  No	Include the use of human fetal tissue, human embryos, or embryonic stem cells?	Contact OBAO for submission instructions and guidance	
 Yes  No	Include PHI or are you requesting a HIPAA waiver?	If yes, HIPCO will conduct a review of this protocol. Contact: [contact]	
 Yes  No	Use data from CTSI Best Practices Integrated Informatics Core (BPIC) Formerly the AHC Information Exchange	The Information Exchange ancillary review will be assigned to your study by IRB staff Contact: [contact]	Approval must be received prior to IRB approval.
 Yes  No	Use the Biorepository and Laboratory Services to collect tissue for research?	The BLS ancillary review will be assigned to your study by IRB staff. Contact: [name]	These groups do not have a separate application process but additional information from the study
 Yes  No	Have a PI or study team member with a conflict of interest?	The Col ancillary review will be assigned to your study by IRB staff Contact: [contact]	Does not affect IRB approval.
 Yes  No	Need to be registered on clinicaltrials.gov?	If you select "No" in ETHOS, the clinicaltrials.gov ancillary review will be assigned to your study by IRB staff Contact: [contact]	Does not affect IRB approval.
 Yes  No	Require registration in OnCore?	If you select "No" or "I Don't Know" in ETHOS, the OnCore ancillary review will be assigned to your study by IRB staff	Does not affect IRB approval.

**MEDICAL PROTOCOL (HRP-590)**

**PROTOCOL TITLE:** Combining cerebellar tDCS and constraint-induced language therapy in non-fluent aphasia: a novel approach to target discourse  
**VERSION DATE:** 08/09/2023

**REVISION HISTORY**

Revision #	Version Date	Summary of Changes	Consent Change?
2	8/17/22	Added details re: adverse effects in section 13.0 Modified consenting process will always be in person, section 21.0 Changed population of “fear of negative consequences...” as excluded, section 9.0 Deleted “serious health conditions...” section in section 9.0	yes
3	8/29/2022	Removed population susceptible to coercion”	No
4	12/20/2022	Changed tDCS intervention from cathodal to anodal (per recent evidence) and increased the behavioral intervention from 30 minutes to 45 minutes (per recent evidence). Anodal electrode will be placed over right cerebellum, cathode electrode will be placed over right deltoid (per recent evidence re: placement)  Changed working memory task from Wisconsin Card Sorting task to N-back task (per recent evidence and recommendations from colleagues using these tasks)  Students have just finished training and we finalized the SOP. Recruitment will begin in mid January.	No

**MEDICAL PROTOCOL (HRP-590)**

**PROTOCOL TITLE:** Combining cerebellar tDCS and constraint-induced language therapy in non-fluent aphasia: a novel approach to target discourse

**VERSION DATE:** 08/09/2023

5	08/09/2023	
Remove history of migraine from exclusionary criteria.
 
Change “history of seizures” to history of seizures within the past 12 months.
 
Confirmation of non-fluent aphasia diagnosis is requested to be changed from only physician or clinician report or Assessment using the Western Aphasia Battery to add “informal language assessment conducted by the PI”. Because PI is a certified, licensed speech-language pathologist, characteristics of non-fluent aphasia become apparent during the interaction with the potential participant through questions and answers about the study and through the screening process.
 
Changes made to protocol (pages 20-21) and screening form
	No

# MEDICAL PROTOCOL (HRP-590)

PROTOCOL TITLE: Combining cerebellar tDCS and constraint-induced language therapy in non-fluent aphasia: a novel approach to target discourse

VERSION DATE: 08/09/2023

## **MEDICAL PROTOCOL (HRP-590)**

**PROTOCOL TITLE:** Combining cerebellar tDCS and constraint-induced language therapy in non-fluent aphasia: a novel approach to target discourse

**VERSION DATE:** 08/09/2023

### **ABBREVIATIONS/DEFINITIONS**

Anodal Transcranial Direct Current Stimulation (a-tDCS)

Constraint-induced language therapy (CILT)

Dorsolateral Prefrontal Cortex (DLPFC)

Electroencephalogram (EEG)

Quality of Life (QOL)

Speech-Language Pathologist (SLP)

Transcranial Direct Current Stimulation (t-DCS)

Dento-thalamic-cortical tract (DTC)

Functional magnetic resonance imaging (fMRI)

Principal Investigator (PI)

Clinical Translational Research Services (CTRS)

Biostatistical Design and Analysis Center (BDAC)

Standard Operating Procedures (SOP)

Statistical Package for the Social Sciences (SPSS)

Stroke and Aphasia Quality of Life Scale (SAQOL)

## MEDICAL PROTOCOL (HRP-590)

PROTOCOL TITLE: Combining cerebellar tDCS and constraint-induced language therapy in non-fluent aphasia: a novel approach to target discourse

VERSION DATE: 08/09/2023

### 1. Objectives

#### 1.1. Purpose:

*To determine the effect of combining constraint-induced language therapy (CILT) with cerebellar tDCS in individuals with non-fluent aphasia after stroke.*

*The primary aims are to 1) determine the effect of combining cerebellar tDCS with constraint-induced language therapy (CILT) on language as measured by a verbal fluency task and discourse analysis task in a prospective, crossover study of adults with non-fluent aphasia after a cortical stroke and 2) demonstrate feasibility and data collection to inform a larger study.*

*The secondary aims include impact of the combined intervention on 1) resting state spectral EEG as measured through delta wave percentage 2) working memory as measured by the score on the Wisconsin Card Sorting Test and 3) quality of life as measured by the Stroke Aphasia Quality of Life survey tool. A final secondary aim will be to identify the tolerance of the intervention and barriers to participation measured by the adverse events questionnaire.*

### 2. Background

#### 2.1. Significance of Research Question/Purpose:

*Information gained from this study will drive changes to the methodology for a larger clinical trial that will minimize attrition and help determine robust outcome measures.*

*Non-fluent aphasia occurs after a focal injury to the expressive language regions of the cortex, most often after a stroke and is characterized by limited verbal language and intact comprehension of language. While efficacious behavioral interventions have been identified, they are few and rarely lead to complete language recovery. The loss of effective, efficient expressive language can have a devastating impact on social relationships, return to work, independence and mental health, to name a few.*

*Identification of novel, effective interventions for non-fluent aphasia has been identified as a key research priority in the field of speech-language pathology.*

*Preliminary data will provide valuable information about the potential of combining CILT with right cerebellar anodal tDCS to positively impact language and working memory in non-fluent aphasia. The dento-thalamic-cortical tract (DTC) is the primary pathway between the cerebellum and cortex and has recently been implicated in non-fluent aphasia. A better*

## MEDICAL PROTOCOL (HRP-590)

PROTOCOL TITLE: Combining cerebellar tDCS and constraint-induced language therapy in non-fluent aphasia: a novel approach to target discourse

VERSION DATE: 08/09/2023

*understanding of the role of the DTC and its potential for neuroplastic change after cortical stroke will be included in the interpretation.*

*Neurophysiologic data from EEG will reveal not only the impact of tDCS on alpha and delta bands but the relationship to discourse. Finally, we will be able to document changes to quality of life and determine if changes are related to the experimental intervention.*

*From an educational perspective, this project will provide a valuable inter-professional experience for graduate students from the Departments of Communication Sciences and Disorders and Department of Computer Science. Such cross-college collaborations are an institutional priority on the University of Minnesota, Duluth campus.*

*This body of work has the potential to lead to the development of a new intervention protocol for non-fluent aphasia and provide the neurophysiologic rationale for the changes observed. Together, this will drive the field of neurorehabilitation forward in creating novel, innovative interventions for optimal functional recovery.*

### 2.2. Preliminary Data: N/A

### 2.3. Existing Literature:

*The study of neuroplasticity has provided much needed insight into mechanisms of neural recovery which has launched a shift in the way rehabilitation professionals plan intervention for individuals after stroke and brain injury. Now, greater attention is given to the type and amount of behavioral, task-specific practice that is thought to promote long-term potentiation and experience dependent plasticity. However, functional recovery after stroke and brain injury is still, often incomplete, negatively impacting independence and return to social, vocational and community engagement.*

*Intensity of rehabilitation has been identified as a key research priority by a number of authors (Cherney et al., 2008, 2011; Marangolo, 2020).*

*Specifically, CILT reportedly has an 86% evidence to clinical use gap and therefore, requires additional study (Shrubsole et al., 2018).*

*Another research priority identified by Marangolo and colleagues (2020) was to better determine the potential effects of cerebellar tDCS on language in individuals with aphasia. Many reports have confirmed connectivity between the right cerebellar hemisphere and the left cortex, specifically the frontal and prefrontal cortical regions (Stoodley, 2012). These regions are*

## MEDICAL PROTOCOL (HRP-590)

PROTOCOL TITLE: Combining cerebellar tDCS and constraint-induced language therapy in non-fluent aphasia: a novel approach to target discourse

VERSION DATE: 08/09/2023

*associated with expressive language, motor planning and programming and cognition. In fact, the right cerebellum has been shown to play a role in word retrieval and generation, working memory, language learning and semantic processing (Murdoch, 2010; Stoodley, 2012) and diaschesis in the right cerebellum has been shown in chronic non-fluent aphasia (Abe et al., 1997). This, paired with the distance from the stroke lesion site makes the right cerebellum a desirable location for stimulation. The combination of tDCS behavioral language intervention has resulted in improved naming in individuals with aphasia (Sebastian et al., 2017, 2020; Turkeltaub et al., 2016). However, there has been no evidence regarding other functional language skills such as discourse.*

*Finally, another research priority has been the inclusion of neurophysiologic measures in intervention studies to better understand the neural underpinnings of the experimental intervention (Cherney et al., 2008, 2011). Although functional magnetic resonance imaging is the tool most often recommended, it has many contraindication such as cost, availability, and individual comfort and tolerance. Although EEG acquires different data than fMRI, it is a measure of neurophysiology. It is also non-invasive, more accessible and cost-effective, fairly fast to acquire and well-tolerated. Resting state EEG has been identified as a viable tool to investigate electrical brain activity in those with post-stroke aphasia (Dalton et al., 2021) and is sensitive to changes after tDCS (Boonstra et al., 2016). Since an increase in delta frequency bands has been associated with the language deficits observed in aphasia (Hensel et al., 2004; Spironelli & Angrilli, 2009), one would hypothesize it may be a sensitive measure to determine the neurophysiologic impact of a language intervention such as that in the proposed study. In addition, an increased peak alpha frequency has been associated with improved attention and “cognitive preparedness” which would also be an expected outcome of the proposed intervention.*

*This pilot study has the potential to inform a larger, externally funded clinical trial that may lead to an innovative, novel approach to improve functional language in those with non-fluent aphasia.*

### 3. Study Endpoints/Events/Outcomes

#### 3.1. Primary Endpoint/Event/Outcome:

Primary outcome variables include:

1) *Main Concept Discourse analysis using standardized picture description “Broken Window”, story retell “Cinderella” and procedural narrative “how*

## MEDICAL PROTOCOL (HRP-590)

PROTOCOL TITLE: Combining cerebellar tDCS and constraint-induced language therapy in non-fluent aphasia: a novel approach to target discourse

VERSION DATE: 08/09/2023

*to make a peanut butter sandwich". Each task has established standards and a scoring system for responses. Scoring is categorical and includes: accurate and complete =3, accurate and incomplete =2, inaccurate and complete =2, inaccurate and incomplete =1 and absent response =0 (Richardson & Dalton, 2016). Hypothesis: We hypothesize the raw score of each of the discourse measures (picture, story and procedure) will significantly increase after the real tDCS intervention, but not after the sham intervention.*

*2) Verbal Fluency is assessed by asking the participant to name as many animals as they can in one minute and then as many words that start with /f/ as they can in one minute. The tester collects a tally of how many animals and words that begin with /f/ were produced by the participant which is used as a raw score, scaled. If the participant names items that are not within those categories, those responses are not counted in the tally. These tasks are valid and reliable and used throughout aphasia literature.*

*Hypothesis: We hypothesize the raw score of the verbal fluency measures will significantly increase after the real tDCS intervention, but not after the sham intervention.*

*These data will be collected at four points in time:*

- 1) Initial baseline;
- 2) post intervention (A or B);
- 3) Follow-up baseline (after washout period);
- 4) post intervention (A or B)

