### 3.2. Secondary Endpoint(s)/Event(s)/Outcome(s):

1. Working memory has been shown to play a role in non-fluent aphasia. Working memory is assessed using the N-back task. Scoring is binary and each response is either scored as correct =1 or incorrect =0 to obtain a raw score that is a scaled variable. We are interested in learning if the working memory score changes after intervention and if the change has a relationship with any changes in language as measured above in the primary endpoint.

*Hypothesis: We hypothesize the working memory score will significantly increase after the real tDCS intervention, but not after the sham intervention. We also hypothesize a significant positive relationship between the working memory score and the scores across all three discourse tasks.*

*These data will be collected at four points in time:*

- 1) Initial baseline;
- 2) Post intervention (A or B);

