## MEDICAL PROTOCOL (HRP-590)

PROTOCOL TITLE: Combining cerebellar tDCS and constraint-induced language therapy in non-fluent aphasia: a novel approach to target discourse

VERSION DATE: 08/09/2023

- 3) Follow-up baseline (after washout period);
- 4) Post intervention (A or B)

2. An increase in delta wave percentage during resting state EEG has been shown in individuals with aphasia. The standard practice is to conduct a 2 minute resting state EEG while eyes are open. Data is then processed through EEGLab in MATLAB to “pull out” the amount of delta wave bands/total wave bands to identify a percentage of delta waves within the 2 minute sample. We are interested in learning if this delta percentage changes after intervention and if the change may be associated with any changes in language as measured above in the primary endpoint. The delta wave value is calculated by dividing the number of delta waves present/total waves within the 2 minute sample and represented in a percentage. The delta wave percentage will be calculated for each of the following EEG locations: Fp1, F3, F7 and Fz of the 10/20 International EEG system. This would provide a neurophysiologic rationale for the changes in language.

*Hypothesis: We hypothesize the delta percentage to significantly decrease after the real tDCS intervention, but not after the sham intervention. We also hypothesize a significant negative correlation between the delta percentage and scores across the discourse tasks, with lower delta wave percentage, language scores will be higher.*

These data will be collected at four points in time:

- 1) Initial baseline;
- 2) Post intervention (A or B);
- 3) Follow-up baseline (after washout period);
- 4) Post intervention (A or B)

3. Quality of Life will be assessed using an abbreviated version of the Stroke and Aphasia Quality of Life Scale-39 (SAQOL-39) (Hilari et al., 2003) , which uses a Likert Scale 1-5. Completion of the SS-QOL results in a raw score, which will be a scaled variable. We are interested in the relationship between QOL and changes in language as measured above. *Hypothesis: We hypothesize the raw score of the SAQOL will significantly increase after the real tDCS intervention, but not after the sham intervention. We also hypothesize the score on the SAQOL will be positively and significantly correlated with scores across the discourse tasks.*

These data will be collected at four points in time:

- 1) Initial baseline;

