### 4. Study Intervention(s)/Investigational Agent(s)

#### 4.1. Description:

There will be two intervention conditions in this study:

- 1) anodal tDCS (2mA) to the right cerebellum; and
- 2) sham tDCS to the right cerebellum.

The participants will receive 20 minutes of tDCS (sham or real) during constraint-induced language therapy (CILT) followed by an additional 20 minutes of CILT alone.

tDCS (TCT Research Limited; Hong Kong): 5x5 saline-soaked sponge electrodes will be used with the anode placed over the right cerebellar hemisphere; 1cm under and 4cm lateral of the inion targeting lobule VII and the anode will be placed on the right shoulder (Ferrucci et al., 2015; Sebastian et al., 2020). The electrode placement will be the same across both conditions.

CILT: The CILT behavioral intervention will be led by a certified, licensed speech-language pathologist and a graduate student assistant and will follow the guidelines of CILT (Maher et al., 2006; Mozeiko et al., 2016; Pulvermuller et al., 2001). During the behavioral language intervention, participants will engage in language activities such as card games that require verbal expression. Other forms of communication such as gestures and writing will be discouraged and only verbal output will be encouraged through the use of cues and, when needed, models.

As this is a within subject study, all participants will experience both intervention conditions through a cross over design. Each condition will

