## MEDICAL PROTOCOL (HRP-590)

PROTOCOL TITLE: Combining cerebellar tDCS and constraint-induced language therapy in non-fluent aphasia: a novel approach to target discourse

VERSION DATE: 08/09/2023

*open-ended questions regarding barriers to participation will be analyzed to identify common themes.*

- Primary outcome measures, main concept discourse scores and verbal fluency counts, will be compared between treatment conditions using mixed effects generalized linear models, with fixed effects for treatment, period, sequence, pre-post time point, and treatment by pre-post time point interaction, and random effects for participant within sequence. This will provide difference-in-differences (post-treatment minus pre-treatment) estimates for the treatment effect which will be reported along with 95% confidence intervals as a measure of precision. Similar models will be used to analyze the secondary outcome measures including WI card sorting task, EEG delta wave, and SAQOLL.*
- Estimates from these models will provide important information for planning a well-powered clinical trial that are not obtainable elsewhere. Estimates that will be gathered in this pilot trial that will inform the subsequent power calculation include the treatment effect size, within-participant correlation of repeated measures, and random effects variance, for each of the outcome measures.*
- Pearson's Correlation will be conducted to determine the relationship between primary outcome variables (discourse and working memory scores) and SS-QOL as well as other scaled demographic variables such as age and duration since stroke.*
- Spearman's Rho Correlation analyses will be conducted to determine the relationships between primary outcome variables (discourse and working memory) and EEG data, reported in percentage.*
- The multivariate repeated measures and correlation analyses may not be terribly informative as the pilot sample size may lack the power for these statistics. However, they may be useful in descriptive interpretation of the data and lay the foundation for the larger clinical trial.*

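### The hypotheses in sections 3.1 and 3.2 compare two within-condition significance verdicts and do not match the difference-in-differences that section 15.3 correctly plans

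*Combined protocol and SAP*

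**What the plan says.** Section 3.1 states for the three discourse tasks that the raw score "will significantly increase after the real tDCS intervention, but not after the sham intervention", and repeats the form for the second primary outcome: "We hypothesize the raw score of the verbal fluency measures will significantly increase after the real tDCS intervention, but not after the sham intervention". Section 3.2 does the same for working memory ("the working memory score will significantly increase after the real tDCS intervention, but not after the sham intervention") and, with the sign reversed, for EEG ("the delta percentage to significantly decrease after the real tDCS intervention, but not after the sham intervention"). The SAQOL hypothesis has the same form. The adverse-event survey carries no such hypothesis.

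Section 4.1 gives CILT in both conditions; only the stimulation is real or sham.

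Section 15.3 compares the conditions directly in a mixed model with a treatment by pre-post interaction: "This will provide difference-in-differences (post-treatment minus pre-treatment) estimates for the treatment effect", reported with 95% confidence intervals. Similar models serve the secondary outcomes. It plans no significance test within either condition. No section calls the section 3 wording a success criterion, and none says the hypotheses are to be judged on the interaction.

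**The concern.** A significant change in one condition and a non-significant change in the other is not evidence that the two changes differ. With so few participants, a non-significant sham change is weak evidence of no change.

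The design sharpens this in two ways. If CILT works about equally in both phases, chance alone can make one phase significant and the other not, and the hypothesis would seem supported. If CILT works well enough to make the sham phase significant, the hypothesis is contradicted whatever tDCS adds. A report that answers the section 3 hypotheses literally could therefore reach a different conclusion from the section 15.3 estimate on the same data, and the plan does not say which answers the question.

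**Working it through.** **Inputs.** From section 15.2: n = 4, two-sided 5%, within-participant correlation ρ from 0.4 to 0.9, effect sizes d = 0.9 and 2.3 in units of the between-participant SD. From section 10.1: 5 enrolled, goal of 3 completers. The documents give no SDs for the outcomes. The true gains and the correlation between the two phases' change scores are assumptions. Data are taken as normal with no period or carry-over effect, and the direct contrast is simulated as a paired t-test on each participant's difference in changes.

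**1. The plan's own figure.** For a paired comparison of two measurements, the SD of the difference is √(2(1−ρ)) and the noncentrality is d√n/SD, with 3 df and critical t 3.182.
- ρ = 0.4: SD = √1.2 = 1.095; 2.3 × 2/1.095 = 4.20; power 0.791.
- ρ = 0.9: SD = √0.2 = 0.447; 0.9 × 2/0.447 = 4.02; power 0.760.

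The d detectable at 80% power is 2.33 and 0.95, so the stated 2.3 and 0.9 are reproduced to rounding. The inputs are being read as intended.

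**2. False pattern, closed form.** If both conditions have the same true gain, each phase is significant with probability p and the phases are independent, then

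P(real significant, sham not) = p(1−p).

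This is 0.024 at p = 0.025, 0.16 at p = 0.2 or 0.8, and 0.25 at most, at p = 0.5.

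**3. False pattern, simulated.** n = 4, equal true gains from 0 to 4 SD of change, at least 60,000 runs per setting:

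| Correlation of the two changes | No change in either condition | Maximum over gains |
|---|---|---|
| 0 | 2.4% | 24.7% |
| 0.5 | 2.2% | 19.3% |
| 0.8 | 1.8% | 12.8% |
| −0.5 | 2.5% | 25.6% |

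The direct contrast favours real tDCS in about 2.5% throughout. With n = 3 the maxima at correlations 0, 0.5 and 0.8 are 25.1%, 20.6% and 14.1%; with n = 5 they are 24.4%, 18.8% and 12.1%.

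**4. When CILT itself works.** Take four equally correlated measurements. The two changes are then uncorrelated (covariance ρ−ρ−ρ+ρ = 0), so

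P(pattern) = P(real significant) × [1 − P(sham significant)].

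With a CILT gain of 1.0 SD:
- ρ = 0.9, added benefit 0.9 SD: the sham noncentrality is 1.0 × 2/0.447 = 4.47, power 0.834. The real gain is 1.9 SD, power 0.999. Pattern: 0.999 × 0.166 = 17%.
- ρ = 0.4, added benefit 2.3 SD: the sham noncentrality is 1.0 × 2/1.095 = 1.83, power 0.251. The real gain is 3.3 SD, power 0.968. Pattern: 0.968 × 0.749 = 72%.

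Simulation agrees and adds other gains:

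| ρ | Added benefit | CILT gain | Pattern met | Direct contrast |
|---|---|---|---|---|
| 0.9 | 0.9 SD | 0 | 74% | 49% |
| 0.9 | 0.9 SD | 0.5 SD | 64% | 49% |
| 0.9 | 0.9 SD | 1.0 SD | 17% | 49% |
| 0.9 | 0.9 SD | 1.5 SD | 1% | 49% |
| 0.7 | 1.6 SD (assumed) | 1.0 SD | 57% | 51% |
| 0.7 | 1.6 SD (assumed) | 1.5 SD | 27% | 51% |
| 0.4 | 2.3 SD | 1.0 SD | 72% | 53% |
| 0.4 | 2.3 SD | 1.5 SD | 53% | 53% |

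The direct contrast does not move with the CILT gain, because that gain cancels in the difference of changes. Where the pattern is met more often than the direct contrast is significant, that is not better power: the same rule yields the false rates in step 3.

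**The case against.** The best defence is that section 3 holds hypotheses, not decision rules, and that the analysis is in section 15.3, which is right. A reader might infer that the protocol counts this pattern as success, or that the trial runs a 25% false-positive risk. The documents support neither: no success criterion is written, no within-condition test is planned, and the interaction estimate does not carry the error.

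The 25% is also a ceiling. It needs equal gains, about 50% power in each phase and uncorrelated changes. People who respond to CILT in both phases would make the changes positively correlated and bring the rate down. If the discourse hypothesis requires all three tasks to show the pattern, the maximum for that outcome falls to 1.6%, 4.2% or 9.5% at assumed between-task correlations of 0, 0.5 or 0.8.

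Nor does the hypothesis fail whenever CILT works. It fails when the sham gain reaches significance, which 4 participants will often not achieve; the collapse to 17% and 1% belongs to ρ = 0.9.

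Finally, this is a pilot that concedes it may lack power. Its stated inputs to the larger trial are an effect size, a correlation and a variance, not a significance pattern, so a misdirected larger trial is a possibility and not a forecast.

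All of this stands and limits the size of the point. It does not remove the mismatch: the five hypotheses as worded ask something that section 15.3 does not answer, and no sentence connects them.

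**Conclusion.** The point holds as an inconsistency between the hypotheses and the analysis, with a real risk of misreading the results; it is not a fault in the planned treatment estimate. Answered as worded, with n = 4 and equal true gains, the hypotheses would falsely favour real tDCS in about 2% of trials if nothing changes, up to about 12 to 20% with positively correlated changes, and up to about 25% with independent ones, against 2.5% for the direct contrast. In the other direction, a true added benefit can be missed because the sham phase also improves significantly; at a CILT gain of 1.0 SD the pattern is met in anything from 17% to 72% of trials across the plan's correlation range. These rates are per outcome and rest on gains and change-score correlations that the documents do not give. The change is worth making because it is nearly free.

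**What to change.** Reword the five hypothesis sentences in sections 3.1 and 3.2 to say that the pre-to-post change is larger (for delta, a larger decrease) in the real than in the sham condition. Add one sentence saying that each is judged on the treatment by pre-post interaction estimate and its 95% confidence interval from section 15.3. Report within-condition changes descriptively, without significance tests. The cost is a text amendment; data collection and the model stay as they are.
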